543 13. Participation in another clinical trial

544 14. Persons with any kind of dependency on the investigator or employed by the
545 responsible institution or investigator

546 15. Persons held in an institution by legal or official order

547

548 **4.4. Withdrawal of trial subjects after trial start**

549 Once a patient has been included in the study the investigator will make every reasonable
550 effort to keep the patient in the study. However, if the investigator has to withdraw a patient
551 from study or if the patient refuses further study participation, a final examination should be

552 performed. For patients withdrawn from the study, the follow-up information should be
553 obtained, if possible.

554 A patient may request to be withdrawn from the study protocol at any time, for any reason,
555 without prejudice. A patient may also be withdrawn from the protocol at the request of his/her
556 physician, for any reason.

557 **4.4.1. Procedures for premature withdrawal from treatment during the**
558 **trial**

559 The active study participation stops with the start of RRT. Patients who withdraw from active
560 study participation will be requested to permit continued data collection for the remainder of
561 the follow-up period.

562 **4.5. Closure of trial sites/Premature termination of the clinical trial**

563 **4.5.1. Closure of trial sites or premature termination of trial**

564 The sponsor has the right to terminate the study. Reasons, which may require termination,
565 are:

- 566 • Patient enrolment is too slow
- 567 • The investigator fails to comply with the study protocol or legal requirements
- 568 • Data recording is not accurate, e.g. CRFs are not completely filled-in or entries
569 are not legible.

570 **4.5.2. Premature termination of trial**

571 The institution has the right to terminate the trial prematurely if there are any relevant medical
572 or ethical concerns, or if completing the trial is no longer practicable. If such action is taken,
573 the reasons for terminating the trial must be documented in detail. All trial subjects still under
574 treatment at the time of termination must undergo a final examination, which must be
575 documented. The PCI must be informed without delay if any investigator has ethical
576 concerns about continuation of the trial.

577 Premature termination of the trial will be considered if:

- 578 • The risk-benefit balance for the trial subject changes markedly
- 579 • It is no longer ethical to continue treatment

- 580 • The responsible institution considers that the trial must be discontinued for safety
581 reasons (e.g. on the advice of the DMC)
- 582 • An interim analysis or results of other research show that one of the trial
583 treatments is superior or inferior to another
- 584 • It is no longer practicable to complete the trial

585 The responsible institution decides on whether to discontinue the trial in consultation with the
586 PCI, DMC, Advisory Board and/or statistician.

587 **4.6. Treatment**

588 **4.6.1. Treatments to be given**

589 Early initiation of RRT will be initiated at stage 2 of the KDIGO classification

- 590 • urinary output < 0.5mL/kg/h for ≥12h or 2 fold increase of the serum creatinine level
591 compared to the baseline value

592 Late initiation of RRT will be initiated at the stage 3 of the KDIGO classification or if absolute
593 indications for RRT are present

- 594 • KDIGO stage 3:
- 595 ○ urinary output < 0.3 mL/kg/h for ≥24h and/or
 - 596 ○ >3 fold increase of the serum creatinine level compared to the baseline value
597 and/or
 - 598 ○ serum creatinine of more than or equal to 4.0 mg/dL with an acute increase of
599 at least 0.5 mg/dL
- 600 • Absolute indications:
- 601 ○ urea serum levels > 100mg/dL
 - 602 ○ potassium serum levels > 6mmol/L and/or ECG abnormalities
 - 603 ○ magnesium serum levels > 4mmol/L and/or anuria/absence of deep tendon
604 reflexes
 - 605 ○ blood pH < 7.15
 - 606 ○ urine production < 200mL/12h or anuria
 - 607 ○ organ edema in the presence of AKI resistant to diurectic treatment.

608 In order to ensure uniformity of treatment and between the early and the late group, it is
609 critical that specific protocols for the performance of renal replacement therapy be strictly
610 adhered to.

611

612

613 **Modality of RRT**

614 All patients in both groups will be treated using continuous venovenous hemodiafiltration
615 (CVVHDF). Replacement fluid will be delivered into the extracorporeal circuit before the filter
616 (i.e. predilution), with a ratio of dialysate to replacement fluid of 1:1.

617 Dose: The effluent flow prescribed will be based on the patient's body weight at the time of
618 randomization and will be 30 mL per kilogram per hour^{8,44}. Blood flow will be kept above 110
619 mL per minute. Fluid will be removed by decreasing the flow of the replacement fluid and of
620 the dialysate in equal proportion. The delivered dose of RRT will be monitored based on
621 blood-side urea kinetics.

622 Anticoagulation: Regional anticoagulation with citrate will be used to prevent circuit clotting.

623 Cessation of RRT: RRT will be discontinued if renal recovery defined by urine output (> 400
624 mL/24h without or 2100ml/24h with diuretic treatment) and creatinine clearance (> 20
625 mL/min) occurs².

626 **Additional Treatments**

627 The patient's primary physicians will determine the remainder of patient management
628 consistent with established best practices with the management of critically ill patients. In
629 patients with acute lung injury or the acute respiratory distress syndrome, tidal volume for
630 mechanical ventilation will be approximately 6 mL per kilogram of predicted body weight and
631 adjusted to maintain a peak plateau pressure between 25 and 30 cm of water⁵⁰. Ventilator
632 associated pneumonia will be evaluated and treated in accordance with published clinical
633 practice guidelines and consensus statements⁵¹. All medications will be dose adjusted for
634 renal failure and renal replacement therapy in accordance with standard dosing guidelines.

635 All patients will be prescribed a nutritional intake that will provide at least 25-30 kcal/kg/day,
636 depending on mechanical ventilation and other factors. Protein intake will be at least 1.2
637 g/kg/day. In patients receiving parenteral nutrition, carbohydrate infusion rates will not
638 exceed 5 mg/kg/min. Water-soluble vitamins will be supplemented to replace dialysis-related
639 losses.

640 Follow-up per patient: Up to 1 year after randomization.

641

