291 defined as discharge from acute care, whether to acute rehabilitation, transitional care, long-
292 term care or home.

293 • SOFA Organ Failure Scores at days 1-14, day 21 and day 28

294 Non-renal organ system failures will be assessed on the basis of SOFA Organ Failure
295 Scores at days 1-14, day 21 and day 28 following randomization. Organ failure will be
296 defined as an individual SOFA organ failure score ≥ 2 . Parameters to be monitored will
297 include the maximum number of non-renal organ failures, the rates of individual non-renal
298 organ-system failures, the time course of non-renal organ failures, and the overall non-renal
299 SOFA score.

300

301

302 **Economic Analysis**

303 An economic analysis will be conducted to evaluate:

- 304
 - Renal replacement therapy-specific cost of care

305 **ADD-on study**

- 306
 - To evaluate new biomarkers of acute kidney injury, investigate mediators modulating
- 307 mediators (pro- and anti-inflammatory mediators) and leukocyte function, an add-on
- 308 study will be performed. Blood and urine samples from recruited patients will be
- 309 collected and analysed.

310

311 **3. Organisational and administrative aspects of the trial**

312 **3.1. Sponsor**

313 Sponsor : University Hospital Muenster
314 [name]
315 [name]
316 Germany

317 **3.2. Principal Coordinating Investigator**

318 Principal Coordinating
319 Investigator (PCI): **Univ. [name]. [name]**
320 Department of Anesthesiology, Intensive Care and Pain
321 Medicine
322 University Hospital Muenster
323 [name]
324 [name]
325 Germany

326 **3.3. Statistics**

327 Statistician: [name]
328 Institute of Biostatistics and Clinical Research
329 University of Muenster
330 [name]
331 [name]
332 Germany

333 **3.4. Study laboratories and other technical services**

334 Leukocyte Adhesion Laboratory
335 [name]. [name]
336 Department of Anesthesiology, Intensive Care and Pain Medicine
337 University Hospital Muenster
338 [name]

339 [name]

340 **3.5. Central organisation units**

341 Project management: [name]
342 Department of Anesthesiology, Intensive Care and Pain
343 Medicine
344 University Hospital Muenster
345 [name]
346 [name]
347 [contact]
348 [contact]
349 Email: [contact]

350 **3.6. Investigators and trial sites**

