 386 patients receiving care in the critical care units on a daily basis. After obtaining informed
 387 consent and check the randomization criteria, the patient will be registered and
 388 randomization will be carried out by the Institute of Biostatistics and Clinical Research
 389 Münster. Before initiating RRT, laboratory test will be performed and different variables will
 390 be documented including demographic data, APACHE II score, SOFA organ-system score,
 391 etc. In the 'early' group, RRT will be initiated immediately after randomization, whereas
 392 initiation of RRT in the 'late' group will be started after reaching stage 3 of the KDIGO
 393 classification and/or if absolute indications for RRT will be present. Laboratory tests will be
 394 analyzed and variables relevant for the assessment of illness severity will be recorded.

395 SOFA Organ Failure Score at different days, length of ICU stay, length of hospitalization, 28-
396 day all cause mortality, recovery of renal function and requirement for hemodialysis after day
397 28 and day 60, duration of renal replacement therapy, 60-day all cause mortality, 90-day all
398 cause mortality, cost analysis of renal replacement therapy, and 1 year mortality will be
399 documented at follow-up visits up to one year. * Absolute indications for the initiation of RRT
400 are 1) urea serum levels > 100mg/dl, 2) potassium serum levels > 6mmol/l and/or ECG
401 abnormalities, 3) magnesium serum levels > 4mmol/l and/or anuria/absence of deep tendon
402 reflexes, 4) blood pH < 7.15, 5) urine production < 200ml/12h or anuria, and 6) organ edema
403 in the presence of AKI resistant to diuretic treatment ⁴⁴.

404 **4.2. Discussion of trial design**

405 Renal replacement therapy is the main treatment option for AKI. To investigate the
406 appropriate time point of initiation of RRT, we will randomly assign patients to receive early
407 (KDIGO stage 2) or late (KDIGO stage 3 or if absolute indications for RRT are present)
408 initiation of RRT. A placebo group of patients with acute kidney injury withheld from RRT is
409 ethically not acceptable. The currently accepted, absolute indications for the initiation of RRT
410 are

- 411 1) urea serum levels > 100mg/dL,
- 412 2) potassium serum levels > 6mmol/L and/or ECG abnormalities,
- 413 3) magnesium serum levels > 4mmol/L and/or anuria/absence of deep tendon
414 reflexes,
- 415 4) blood pH < 7.15,
- 416 5) urine production < 200mL/12h or anuria, and

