503 We expect a gender distribution of (male:female) 70 :30³⁷. No patient will be excluded from
504 the study on the basis of gender. Gender will be used for covariate adjustment in the final
505 analysis. A subgroup analysis will be performed according to gender (see section 6.1.4).

506 **4.3.1. Inclusion criteria**

- 507 1. Akute Kidney Injury: stage 2 of KDIGO classification
- 508 ○ Urine output of < 0.5 mL/kg/h for ≥ 12 h and/or
 - 509 ○ 2-2.9 -fold increase of the serum creatinine level compared to the baseline
 - 510 value)
- 511 Despite optimal resuscitation
- 512 ○ Optimizing intravascular volume (fluid resuscitation: pulmonary artery artery
 - 513 occlusion pressure/central venous pressure of > 12 mm Hg)
 - 514 ○ Optimization of cardiac index (> 2.6 L/min/m²)
 - 515 ○ Hemodynamic optimization (mean arterial pressure > 65 mmHg)
 - 516 ○ Normalizing intra-abdominal pressure (< 15 mmHg)
- 517 2. At least one of the following conditions:
- 518 ○ Severe sepsis
 - 519 ○ Use of catecholamines (norepinephrine or epinephrine > 0.1 µg/kg/min)
 - 520 ○ Refractory fluid overload (worsening pulmonary edema: PaO₂/FiO₂ < 300
 - 521 mgHg and/or fluid balance > 10% of body weight
 - 522 ○ Development or progression of non-renal organ-dysfunction (SOFA organ
 - 523 system score ≥ 2)
- 524 3. Age between 18 and 90 years
- 525 4. Intention to provide full intensive care treatment for at least 3 days

526 5. Existence of informed consent

527 **4.3.2. Randomization criteria**

528 1. Plasma Neutrophil Gelatinase-Associated Lipocalin (NGAL) > 150 ng/dL

529 **4.3.3. Exclusion criteria**

530 1. Patients with pre-existing kidney disease not requiring RRT (GFR < 30 mL/min)

531 2. Patients who had received any previous renal replacement therapy

532 3. AKI caused by permanent occlusion or surgical lesion of the renal artery

533 4. AKI caused by (glomerulo)nephritis, interstitial nephritis or vasculitis

534 5. AKI caused by postrenal obstruction

535 6. Haemolytic-uremic syndrome / thrombotic thrombocytopenic purpura

536 7. Prior kidney transplant

537 8. hepatorenal syndrome

538 9. AIDS with a CD4 count of < 0.05 x 10⁹/L

539 10. hematologic malignancy with neutrophils of < 0.05 x 10⁹/L

540 11. No hemofiltration machine free for use at the moment of inclusion

541 12. Pregnancy (female patients must be surgically sterile or postmenopausal for at least
542 two years or if of childbearing potential must have a negative serum pregnancy test)

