690 • **Duration of renal replacement therapy [d]**

691 The duration of renal support will be defined as the number of days from the initiation of
692 renal replacement therapy to final dialysis treatment. Duration of renal support will be
693 censored if the patient is still dialysis dependent at the time of death. Duration of renal
694 support will be evaluated on the basis of both the mean number of days of renal support
695 and Kaplan-Meier survival, censored for patient death. The optimal outcome in acute
696 renal failure is the ability of the patient to return to his or her prior living situation not
697 requiring renal replacement therapy on an ongoing basis

698

699

700

701

702 • **Renal replacement therapy data**

703 The following data will be collected

704 - CVVHDF

- 705 ○ Hemodiafilter
- 706 ○ Blood flow
- 707 ○ Dialysate flow
- 708 ○ Replacement fluid rate
- 709 ○ Ultrafiltration rate
- 710 ○ Hours of therapy
- 711 ○ 24-h effluent volume

712 - Complications of therapy

- 713 ○ First use reaction
- 714 ○ Hypotension requiring discontinuation of treatment
- 715 ○ Air embolism
- 716 ○ Bleeding
- 717 ○ New onset of serious arrhythmia during treatment
- 718 ○ Iatrogenic fluid and/or electrolyte disturbance
- 719 ○ Seizures
- 720 ○ Catheter insertion complication

721 - Indications for termination of renal support

722 • **Recovery of renal function by day 28 and 60**

723 Recovery of renal function will be defined as lack of need for continuing dialysis support,
724 and will be classified as complete recovery, partial recovery or no recovery.

- 725 - Complete recovery of renal function will be defined as a serum creatinine that is
726 no more than 0.5 mg/dL greater than baseline.
- 727 - Partial recovery will be defined as a serum creatinine > 0.5 mg/dL greater than
728 baseline but not dialysis-dependent.
- 729 - Patients who remained dialysis dependent at study completion or at time of death
730 will be categorized as having no recovery of renal function.

731 Multiple studies have demonstrated that the majority of patients who recover renal
732 function following ARF do so within the first 4 weeks⁴⁰⁻⁴², justifying the use of the 28-day
733 and 60-day time points.

734

735

736 • **SOFA Organ Failure Scores at day 1-14, 21 and 28**

737 Non-renal organ system failures will be assessed on the basis of SOFA Organ Failure
738 Scores at days 1-14, day 21 and day 28 following randomization. Organ failure will be

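### Two of the four SOFA organ-failure parameters do not separate failures present at randomisation from new ones, and the maximum count cannot register recovery (minor)

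*Protocol*

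**What the plan says.** Protocol 2.3, repeated in 4.7.1.2, makes the SOFA scores a secondary endpoint: "Non-renal organ system failures will be assessed on the basis of SOFA Organ Failure" "Scores at days 1-14, day 21 and day 28 following randomization". Failure of a system is "defined as an individual SOFA organ failure score ≥ 2". Four parameters follow. The first two "include the maximum number of non-renal organ failures, the rates of individual non-renal" systems. The sentence then continues: "organ-system failures, the time course of non-renal organ failures, and the overall non-renal" SOFA score. None of the four is defined relative to a baseline value.

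The same cut-off appears at entry. Section 4.3.1 requires "At least one of the following conditions", and the fourth condition reads "Development or progression of non-renal organ-dysfunction (SOFA organ" system score of 2 or more). The other three are severe sepsis, catecholamine use above a stated rate, and refractory fluid overload, which includes a PaO2/FiO2 limit of 300.

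Baseline SOFA is available. The text on Figure 1 says that before RRT starts, variables will "be documented including demographic data, APACHE II score, SOFA organ-system score", and Table 3 marks SOFA at screening and at baseline. Allocation is balanced on cardiovascular SOFA (0-2 versus 3-4) and oliguria (4.2.1). Section 6.1.3 describes the analysis of secondary endpoints only in general terms, and the synopsis calls everything beyond the primary analysis explorative.

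**The concern.** Section 2.1 argues that early RRT may limit injury to organs other than the kidney. That concerns failures that arise, worsen or resolve after randomisation. The first two parameters mix these with failures that were already there. A patient who enters through the SOFA condition has a failing non-renal system by definition, and the other three routes also point to circulatory or respiratory trouble. Many patients may therefore contribute an outcome event on day 1 that treatment could not have prevented.

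At stake is how clearly these two parameters can be read and how precisely the arms can be compared on them. Prevalent failures add variation between patients that has nothing to do with treatment. The primary endpoint, the sample size and the confirmatory conclusion are not affected.

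**Working it through.** **What follows from the text alone.** The maximum is taken over days 1-14, 21 and 28, so it is at least the day 1 count. A patient with three failing systems on day 1 who clears all of them scores 3. So does a patient who keeps all three and gains none. The individual rates likewise count any system scored 2 or more on day 1, whether it failed before or after randomisation. Neither statement needs an assumption.

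**Size of the precision loss.** The protocol gives no baseline SOFA distribution and no failure rates, so every rate below is an assumption. Take five non-renal systems and 125 patients per arm (250 recruited). A share p of systems has failed at entry. In unaffected systems, new failure occurs in 30% (late) or 20% (early). Deaths are ignored and baseline failures are taken to persist to day 1, so the maximum equals the baseline count plus new failures.

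Hand check at p = 0.5 with independent systems:
- Difference in means: 5 × 0.5 × (0.30 − 0.20) = 0.25 failures.
- Raw maximum: a system is ever failed with probability 0.5 + 0.5 × 0.30 = 0.65 (late) or 0.5 + 0.5 × 0.20 = 0.60 (early). Variances are 5 × 0.65 × 0.35 = 1.1375 and 5 × 0.60 × 0.40 = 1.20. SE = √((1.1375 + 1.20)/125) = 0.137. z = 0.25/0.137 = 1.83. Power ≈ Φ(1.83 − 1.96) = 45%.
- Given the baseline count, only the new failures vary: 2.5 × 0.30 × 0.70 = 0.525 and 2.5 × 0.20 × 0.80 = 0.40. SE = √(0.925/125) = 0.086. z = 2.91. Power ≈ Φ(2.91 − 1.96) = 83%.

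Simulation with baseline failures correlated within patients (random effect SD 0.5 or 1.0 on the logit scale) compared a t-test on the raw maximum with ANCOVA on the baseline count, two-sided 5%. Ranges cover both SDs and repeated runs.

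| Systems failed at entry | Raw maximum | Adjusted for baseline count |
|---|---|---|
| 30% | 53-66% | 91-93% |
| 50% | 32-41% | 81-85% |
| 60% | 24-32% | 72-76% |

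**Recovery versus prevention.** A second simulation let systems recover (10% per day) and fail anew (1% or 3% per day). It used 115 patients per arm (230 analysed), 30%, 50% or 70% of systems failed at entry with at least one per patient, the protocol's visit days and no deaths. Tests were unadjusted.
- Correlation with the baseline count: 0.48-0.82 for the maximum, 0.47-0.60 for the time-averaged count.
- Recovery 1.5 times faster in one arm: power 0.23-0.48 for the maximum, 0.91-0.99 for the time-averaged count.
- New failures halved in one arm: power 0.07-0.96 for the maximum. It is lowest when most systems have failed at entry and new failures are rare, and highest in the opposite case.

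The time-averaged count stands in here for the protocol's time course, whose summary measure the protocol does not specify.

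**The case against.** A reader might infer that the whole organ-failure endpoint mostly re-measures severity at entry and cannot show improvement. The documents do not support that. The sentence in 2.3 goes on to list the time course and the overall non-renal SOFA score, and both distinguish the patient who clears three failures from the one who keeps them. The SOFA entry condition is one of four alternatives, so it does not by itself give every patient a failure at entry. How far the maximum reflects entry severity depends entirely on assumed rates: with few failures at entry and frequent new ones, it detected prevention well.

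Nor does the missing baseline reference bias the comparison. Randomisation protects the unadjusted test, whose error rate already allows for chance imbalance, and allocation also balances cardiovascular SOFA in two bands and oliguria.

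The first simulation also favours adjustment by construction, because treatment acts only on new failures. Its figures illustrate the possible loss and are not a forecast for this trial.

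Finally, covariates are commonly left to the SAP, which was not at hand, so the absence of a stated adjustment is not an error. This stands for the choice of model. It does not dispose of the point, because the protocol itself fixes what counts as an event. Even with a covariate in the SAP, the individual failure rates would still include failures that preceded randomisation.

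**Conclusion.** The point holds in a narrow form. Two of the four parameters mix pre-existing with new failures, and one of these, the maximum, cannot register recovery. Both follow from the definitions. The consequence is lost precision and a blurred reading of an exploratory secondary endpoint, without systematic bias. Under the assumed rates, adjusting the maximum for the baseline count raises power from roughly 24-66% to 72-93%. The true gain depends on baseline and new-failure rates that the protocol does not give, and on deaths, which both simulations leave out although 55% control mortality by day 90 is expected. Priority: minor.

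**What to change.** In Protocol 2.3 and 4.7.1.2:
- Analyse the maximum count and the overall non-renal SOFA score with the corresponding baseline value as covariate. Take that value from the baseline visit in both arms. The last score before RRT will not do, since in the late arm it may fall well after randomisation.
- Report individual organ-failure rates in two parts: new failures (a score of 2 or more in a system scored below 2 at baseline) and failures already present at baseline.
- Keep the time course as the measure of recovery.
- Present the new-failure count as a supplement to the four listed parameters. It should not replace them, because it misses worsening in an organ that is already failing (a rise from 2 to 4, for example), and patients who die early have less time to develop new failures.

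The cost is a few sentences of definition and analysis wording. Baseline SOFA is already in the visit schedule, so no extra visits, data or patients are needed.

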
Principal inclusion criteria:
	
Principal inclusion criteria:
 
1. Critically ill patients with acute kidney injury (KDIGO stage 2-classification) despite optimal resuscitation
○ Urine output of < 0.5 mL/kg/h for ≥ 12 h and/or > 2fold increase of serum creatinine level compared to the baseline value2. At least one of the following conditions
○ Severe sepsis○ Use of catecholamines (norepinephrine or epinephrine > 0.1 µg/kg/min)○ Refractory fluid overload: worsening pulmonary edema: PaO₂/FiO₂ < 300 mmHg and/or fluid balance > 10% of body weight)○ Non-renal SOFA organ system score ≥ 23. 18-90 years old4. Intention to provide full intensive care treatment for at least 3 days5. Written informed consent 
Randomization Criteria:
 
1. Plasma Neutrophil Gelatinase-Associated Lipocalin (NGAL) > 150 ng/dL 
Principal exclusion criteria:
 
1. Pre-existing kidney disease not requiring RRT (GFR < 30 mL/min)2. Previous renal-replacement therapy3. AKI caused by permanent occlusion or surgical lesion of the renal artery4. AKI caused by (glomerulo)nephritis, interstitial nephritis or vasculitis5. AKI caused by postrenal obstruction6. Haemolytic-uremic syndrome/thrombotic thrombocytopenic purpura7. Prior kidney transplant8. Hepatorenal syndrome9. AIDS with a CD4 count of < 0.05 x 10⁹/L10. Hematologic malignancy with neutrophils of < 0.05 x 10⁹/L11. No hemofiltration machine free for use at the moment of inclusion12. Pregnancy13. Participation in another clinical intervention trial14. Persons with any kind of dependency on the investigator or employed by the institution responsible or investigator15. Persons held in an institution by legal or official order
--------------------------------------	---

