5.5. Data protection

886 The provisions of data protection legislation will be observed. It is assured by the responsible
887 institution that all investigational materials and data will be pseudonymised in accordance
888 with data protection legislation before scientific processing.

889 Trial subjects will be informed that their pseudonymised data will be passed on in
890 accordance with provisions for documentation and notification pursuant to § 12 and § 13 of
891 the GCP Regulations to the recipients described there. Subjects who do not agree that the
892 information may be passed on in this way will not be enrolled into the trial.

893 **6. Statistical methods and sample size calculation**

894 **6.1. Statistical and analytical plan**

895 Statistical analyses will be performed according to the principles of the ICH-guideline E9
896 “Statistical Principles for Clinical Trials” using standard statistical software (SAS or SPSS).

897 A group sequential plan according to O’Brian and Fleming with one interim analysis will be
898 applied. In order to maintain a global significance level $\alpha=0.05$, the interim and the final
899 analysis are performed on local significance levels 0.0052 and 0.0480, respectively. Based
900 on the group sequential plan, in the interim analysis the sample size of the final analysis will
901 be re-calculated applying the Inverse Normal method⁵³.

902 In the event of important new discoveries the design of the study may be changed. If an
903 adaptation of the design is necessary, the respective changes may be done according to the
904 conditional rejection error probability method^{54,55}.

905 The randomized groups will be descriptively compared on all baseline variables using
906 summary statistics such as mean and standard deviation, median and quartiles, or frequency
907 and percent, as appropriate. The primary efficacy analysis will include all randomized
908 patients (full analysis set) and will be performed according to the intention-to-treat principle,
909 i.e. all patients are analyzed in the group to which they were randomized. Primary efficacy
910 analysis provides confirmatory statistical evidence.

911 Beyond the primary intention-to-treat analysis of the primary outcome, sensitivity analyses
912 will be performed. In per-protocol analyses only patients without major protocol violations are
913 included. I.e. in particular, the included patients have complete 90-day follow-up (complete

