981 Power calculations are performed based on the primary endpoint, i.e. the overall survival in a
982 90-day follow-up period (90-day all cause mortality). The primary efficacy analysis is
983 intended to show superiority of early versus late initiation of RRT in intensive care patients
984 with acute kidney injury. An upper bound of the required number of patients is determined,
985 assuming that in the worst expected case 10% of recruited patients have completely non-
986 evaluable data.

987 A group sequential plan according to O'Brien and Fleming with one interim analysis and a
988 global (two-sided) significance level $\alpha=0.05$ is applied. The expected 90-day mortality
989 rate in the control group with late initiation of RRT is 55%. Differences between treatment
990 groups are to be detected with a power of 80%, if the 90-day mortality rate in the
991 experimental intervention group with early initiation of RRT is 37% or smaller. The expected
992 treatment effect is substantiated by published data and clinical reasoning. The interim
993 analysis is conducted using half of the total number of patients (information rate 0.5).
994 Resulting from these considerations, interim analysis is performed after 53 deaths have been
995 observed across both treatment groups. The final analysis is performed after 106 deaths
996 have been observed across both treatment groups. I.e. assuming an average 46% mortality
997 rate in the 90-day follow-up period, a total number of $106/0.46=230$ patients across both
998 treatment groups is included in the final analysis. This corresponds to 250 recruited
999 patients. Power calculations were performed using the ADDPLAN software.

1000 **Compliance / Rate of loss to follow up**

1001 Approximately 5-10% of recruited patients are expected to be lost to follow-up during the 90-
1002 day follow-up period. In terms of a worst-case approach in the power analysis, dropout
1003 patients are assumed to have completely non-evaluable data. Therefore in order to ensure
1004 that 240 evaluable patients exist, 260 patients will be recruited. Apart from this worst-case
1005 approach pursued in power calculations, in the primary analysis dropout patients in fact are
1006 included.

1007 **7. Safety**

1008 **7.1. Definitions of adverse events**

1009 **7.1.1. Adverse event**

1010 An adverse event (AE) is any untoward medical occurrence in a trial subject administered an

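### A patient can meet the inclusion criteria and an absolute indication for late-arm RRT at the same moment, and nothing in eligibility addresses this; such patients carry no timing contrast and the sample size does not allow for them

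*Protocol*

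**What the plan says.** **Entry.** Protocol section 4.3.1, criterion 1, requires KDIGO stage 2, shown by "Urine output of < 0.5 mL/kg/h for ≥ 12 h and/or" a creatinine rise of 2 to 2.9 times baseline. The synopsis carries the same stage 2 label but gives the creatinine part as "> 2fold increase of serum creatinine level compared to the baseline value", without a ceiling. Criterion 2 needs one further condition, which may be "Refractory fluid overload (worsening pulmonary edema", defined by oxygenation and/or fluid balance. Section 4.3.2 adds an NGAL threshold. Section 4.3.3 lists 15 exclusions, none of which refers to an existing indication for RRT.

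**Start of RRT.** The text under Figure 1 (section 4.1.1) has the early arm start immediately after randomisation. Under section 4.6.1 the late arm starts at KDIGO stage 3 or when any absolute indication is present. These indications cover urea, potassium, magnesium, pH, "urine production < 200mL/12h or anuria" and "organ edema in the presence of AKI resistant to diurectic treatment".

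**Sample size.** Sections 6.1.5 and 6.2 assume 90-day mortality of 55% (late) and 37% (early), with 80% power, 106 deaths, 230 patients in the analysis and 250 recruited. Section 6.1.2 sorts late-arm patients into those who die before reaching an indication, those who never reach one, and about 80% who reach one during the 90 days.

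**The concern.** The intervention is the timing of RRT and nothing else. A patient who already has an absolute indication at randomisation starts at once whichever arm is drawn, so that patient says nothing about early against late. Section 6.1.2 does not recognise such patients as a class, and section 6.2 makes no allowance for them. If they are more than a handful, the effect that the trial can observe is smaller than the one it was sized for. Contrast lost in this way cannot be recovered after randomisation. Oliguria is a stratification factor (section 4.2.1), so the plan expects low urine output to be common at entry.

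**Working it through.** **1. Do the criteria overlap?**

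The inclusion limit over 12 hours is 0.5 × weight × 12 mL.

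| Weight | Inclusion limit, mL/12 h | 200 mL/12 h expressed as mL/kg/h |
|---|---|---|
| 50 kg | 300 | 0.333 |
| 70 kg | 420 | 0.238 |
| 80 kg | 480 | 0.208 |

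The two limits meet at 200 / (0.5 × 12) = 33.3 kg. Above that weight, anyone below 200 mL in 12 hours satisfies the urine inclusion limit.

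The stage 2 label does not keep this patient out. The urine item for stage 3 in section 4.6.1 needs output below 0.3 mL/kg/h for at least 24 hours. A 70 kg patient at 0.238 mL/kg/h for 12 hours has the absolute indication without meeting that item.

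Urea, potassium, magnesium and pH have no eligibility limit, so an indication on any of them can also be present at entry. The same is possible for diuretic-resistant edema.

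**2. Reproducing the stated design.**

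Inputs from sections 6.1, 6.1.5 and 6.2: mortality 55% and 37%; 1:1 allocation; "global (two-sided) significance level $\alpha=0.05$ is applied"; one interim look at half the information; the interim and final "analysis are performed on local significance levels 0.0052 and 0.0480, respectively".

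- HR = ln(1 − 0.37) / ln(1 − 0.55) = 0.579.
- The two-look O'Brien-Fleming boundary needs a drift of 2.812 for 80% power.
- Schoenfeld: deaths = 4 × 2.812² / (ln 0.579)² = 105.7, so 106. Power at 106 deaths is 80.1%.
- Patients: 106 / 0.46 = 230.4; 230 / 0.92 = 250.

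The figures of 106, 230 and 250 reproduce.

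**3. Adding overlap patients.**

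Two quantities are assumptions, because the document gives neither: the share *f* of patients who already have an indication, and their mortality *m*, taken as equal in both arms. The other patients keep 55% and 37%.

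- Late mortality = (1 − f) × 0.55 + f × m
- Early mortality = (1 − f) × 0.37 + f × m
- HR = ln(1 − early) / ln(1 − late)
- Drift = |ln HR| × √106 / 2, evaluated against the same boundary

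Example with f = 10% and m = 55%: late 0.550; early 0.9 × 0.37 + 0.1 × 0.55 = 0.388; HR = ln(0.612) / ln(0.45) = 0.615; drift 2.50; power 70%.

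| f | HR (m = 55%) | Power at 106 deaths, m = 37 / 55 / 70% | Deaths for 80% power, m = 37 / 55 / 70% | Evaluable patients for 80% power |
|---|---|---|---|---|
| 0 | 0.579 | 80% | 106 | 231 |
| 5% | 0.597 | 76 / 75 / 75% | 117 / 119 / 121 | 257 |
| 10% | 0.615 | 72 / 70 / 69% | 129 / 134 / 139 | 286-288 |
| 20% | 0.652 | 63 / 59 / 57% | 160 / 174 / 184 | 362-365 |
| 30% | 0.691 | 52 / 47 / 45% | 204 / 232 / 250 | 470-477 |

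(In the first row 230.4 is rounded up; the plan states 230.)

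**The case against.** **KDIGO stage 3.** A reader might infer that stage 3 patients are admitted too: the urine limit is open-ended, its link to creatinine is and/or, and the synopsis sets no creatinine ceiling. The documents do not support this. Both places head the criterion with stage 2, and section 4.6.1 makes any single stage 3 item sufficient for stage 3, so such a patient fails the label. What remains is a wording mismatch between the synopsis and 4.3.1.

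**Fluid overload.** A reader might also infer that refractory fluid overload at entry is itself a late-arm trigger. The inclusion condition is defined by oxygenation and/or fluid balance and does not mention diuretics; the trigger is edema resistant to diuretics. They can occur together but do not coincide.

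**Size.** The overlap share is unknown. The 80% in section 6.1.2 carries no timing, so it does not measure overlap at baseline. Section 1 calls some life-saving indications uncommon, but the ones it names are more extreme than the urine and urea thresholds in 4.6.1. The 55% and 37% could be read as already diluted; nothing in section 6 says so.

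**Mitigation.** Daily screening favours finding patients early. The sample size is re-calculated at the interim (section 6.1), so power at a fixed 106 deaths is not the whole picture. The Cox models in section 6.1.2 examine actual RRT timing. These points stand as mitigation, but none removes the overlap. Re-calculation can buy back power only with more patients, and the Cox models are sensitivity analyses.

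**Bias.** The overlap affects both arms alike. It pulls the estimate towards no effect and does not bias the intention-to-treat comparison. This stands, and it limits the severity.

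**Conclusion.** The point holds for the absolute indications. It is clearest for urine below 200 mL in 12 hours, and possible for urea, potassium, magnesium, pH and diuretic-resistant edema. Sections 4.3.1 to 4.3.3 and 4.6.1 are not reconciled on this, and the sample size makes no allowance for it. The cost is lost contrast and power: about 4 to 5 percentage points at a 5% share, 8 to 11 at 10%, and 17 to 23 at 20%. This rests on the assumed shares, on overlap mortality between 37% and 70%, and on the remaining patients keeping 55% versus 37%. A reader might infer from the table that the trial is underpowered by a known amount. The documents do not support that, because they give no share. The arithmetic for 106 deaths is right as it stands. This should be fixed, but it does not undermine the validity of the comparison.

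**What to change.** - Reconcile section 4.3 with section 4.6.1 so that no patient can be randomised while already meeting a late-arm start criterion. Which thresholds apply is for the investigators to decide.
- Count the patients affected in the screening log, so that the share becomes known.
- Make the synopsis creatinine wording identical to section 4.3.1.
- If the overlap is kept on purpose, state the expected share in section 6.2 and restate the power or the number of deaths.

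**Cost.** A short amendment to the eligibility text and the synopsis. Recruitment slows with the share: at the same yield, screening rises by a factor of 1 / (1 − f). That is about 5% more at a 5% share, 11% at 10% (8,439 becomes about 9,380), 25% at 20% and 43% at 30%. With these patients kept out, the stated 106 deaths and 230 patients stand.
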